**Table 4. Response determination for chronic GvHD**

Organ	Complete Response	Partial Response	Progression
Skin	NIH Skin Score 0 after previous involvement	Decrease in NIH Skin Score by 1 or more points	Increase in NIH Skin Score by 1 or more points, except 0 to 1
Eyes	NIH Eye Score 0 after previous involvement	Decrease in NIH Eye Score by 1 or more points	Increase in NIH Eye Score by 1 or more points, except 0 to 1
Mouth	NIH Modified OMRS 0 after previous involvement	Decrease in NIH Modified OMRS of 2 or more points	Increase in NIH Modified OMRS of 2 or more points
Esophagus	NIH Esophagus Score 0 after previous involvement	Decrease in NIH Esophagus Score by 1 or more points	Increase in NIH Esophagus Score by 1 or more points, except 0 to 1
Upper GI	NIH Upper GI Score 0 after previous involvement	Decrease in NIH Upper GI Score by 1 or more points	Increase in NIH Upper GI Score by 1 or more points, except 0 to 1
Lower GI	NIH Lower GI Score 0 after previous involvement	Decrease in NIH Lower GI Score by 1 or more points	Increase in NIH Lower GI Score by 1 or more points, except from 0 to 1
Liver	Normal ALT, alkaline phosphatase, and Total bilirubin after previous elevation of 1 or more	Decrease by 50%	Increase by 2 × ULN
Lungs	- Normal %FEV1 after previous involvement - If PFTs not available, NIH Lung Symptom Score 0 after previous involvement	- Increase by 10% predicted absolute value of %FEV1 - If PFTs not available, decrease in NIH Lung Symptom Score by 1 or more points	- Decrease by 10% predicted absolute value of %FEV1 - If PFTs not available, increase in NIH Lung Symptom Score by 1 or more points, except 0 to 1
Joints and fascia	Both NIH Joint and Fascia Score 0 and P-ROM score 25 after previous involvement by at least 1 measure	Decrease in NIH Joint and Fascia Score by 1 or more points or increase in P-ROM score by 1 point for any site	Increase in NIH Joint and Fascia Score by 1 or more points or decrease in P-ROM score by 1 point for any site
Global	Clinician overall severity score 0	Clinician overall severity score decreases by 2 or more points on a 0-10 scale	Clinician overall severity score increases by 2 or more points on a 0-10 scale

ULN indicates upper limit of normal.

- Resistance is defined as lack of a CR/PR 2 weeks after the last ATO infusion,

[figure not shown]
requirement for alternative therapy or death from GvHD before the last ATO infusion

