## **9.2. Assessment of chronic GvHD**

The clinical stage of chronic GvHD will be assessed in each patient at 6 weeks post-inclusion, then again at 14 weeks and 6 months, then a check-up will be performed at 9, and 12 months post-inclusion. The revised grading system proposed by the NIH (see Appendix 1) will be used (Jagasia et al., 2015). Thus the global scoring of chronic GvHD according to the NIH proposal will be performed (Lee et al., 2015). As far as is possible, a single senior physician, (or fellow with advanced and specific training), at each centre will review the organ status of all patients enrolled in this study. Therefore, for documenting chronic GvHD assessment, the investigator will complete the Chronic GvHD Activity Assessment-Clinician Form A (see Appendix 2). In addition, patients will complete the Chronic GvHD Activity Assessment-Patient self-reported Form B, the “Lee Chronic GvHD Symptom Scale” and the FACT-BMT. The Lee symptom scale was developed as a 30-item symptom scale with 7 subscales to capture the chronic GvHD-specific symptom burden. The symptom scale showed to correlate with patients self-assessed mild, moderate, and severe chronic GvHD manifestations in cross-sectional analysis. Longitudinal assessments showed that changes in overall health status correlated best with changes in quality of life as measured by the FACT-BMT. In contrast, changes in chronic GvHD severity were best detected by changes in the Lee symptom scale.

- **The NIH consensus scoring system** for individual organs is used in this study; Organ sites considered include skin, mouth, eyes, GI tract, liver, lungs, joints and fascia, and female genital tract.
  - For skin, the composite score is split into 2 scores to document the extent of skin involvement (BSA) and the specific skin features, separately (see Appendix 6). The higher of the 2 scores is to be used for computation of global severity.
  - For eyes, scoring from 0 to 3 is based on symptoms, need for eye drops, and use of therapeutic procedure or devices.

- For lung, scoring from 0 to 3 is based on symptoms. In addition, pulmonary function tests to assess FEV1 are mandatory in this protocol. For patients with bronchiolitis obliterans, an absolute improvement in FEV1 of 10% predicted or more is considered a PR as long as the initial FEV1 is < 70%. Normalization ( $\geq$  80%) is considered CR.

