MOUTH Lichen planus-like features present:	 No symptoms	 Mild symptoms with disease signs but not limiting oral intake significantly	 Moderate symptoms with disease signs with partial limitation of oral intake	 Severe symptoms with disease signs on examination with major limitation of oral intake
 Yes  No				
 Abnormality present but explained entirely by non-GVHD documented cause (specify): _____				

**Figure 1.** Organ scoring of chronic GVHD. ECOG indicates Eastern Cooperative Oncology Group; KPS, Karnofsky Performance Status; LPS, Lansky Performance Status; BSA, body surface area; ADL, activities of daily living; LFTs, liver function tests; AP, alkaline phosphatase; ALT, alanine aminotransferase; ULN, normal upper limit. \*Weight loss within 3 months. †Skin scoring should use both percentage of BSA involved by disease signs and the cutaneous features scales. When a discrepancy exists between the percentage of total body surface (BSA) score and the skin feature score, OR if superficial sclerotic features are present (Score 2), but there is impaired mobility or ulceration (Score 3), the higher level should be used for the final skin scoring. \*To be completed by specialist or trained medical providers (see *Supplemental Figure*). \*\*Lung scoring should be performed using both the symptoms and FEV1 scores whenever possible. FEV1 should be used in the final lung scoring where there is discrepancy between symptoms and FEV1 scores.

	SCORE 0	SCORE 1	SCORE 2	SCORE 3
EYES	 No symptoms	 Mild dry eye symptoms not affecting ADL (requirement of lubricant eye drops $\leq 3$ x per day)	 Moderate dry eye symptoms partially affecting ADL (requiring lubricant eye drops $> 3$ x per day or punctal plugs), WITHOUT new vision impairment due to KCS	 Severe dry eye symptoms significantly affecting ADL (special eyewear to relieve pain) OR unable to work because of ocular symptoms OR loss of vision due to KCS
Keratoconjunctivitis sicca (KCS) confirmed by ophthalmologist:	 Yes  No  Not examined			

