8.2 ENDPOINTS

8.2.1 Primary endpoint

The primary endpoint is the evaluation of response rate (CR and PR) at 6 months after the first ATO infusion, with no secondary systemic therapy at any time before M6.

NIH grade of chronic GVHD will be used for the exact definition of this endpoint.

- Complete remission (CR) is defined as complete disappearance of any sign of chronic GvHD
- Partial remission (PR) is defined as improvement of 1 or more point on a 4 to 7-points scale or an improvement of 2 or more points on a 10 to 12-points scale in at least 1 organ or site without progression in any other organ or site.
- More details for response determination are given in the following table:

Organ	Complete Response	Partial Response	Progression
Skin	NIH Skin Score 0 after previous involvement	Decrease in NIH Skin Score by 1 or more points	Increase in NIH Skin Score by 1 or more points, except 0 to 1
Eyes	NIH Eye Score 0 after previous involvement	Decrease in NIH Eye Score by 1 or more points	Increase in NIH Eye Score by 1 or more points, except 0 to 1
Mouth	NIH Modified OMRS 0 after previous involvement	Decrease in NIH Modified OMRS of 2 or more points	Increase in NIH Modified OMRS of 2 or more points
Esophagus	NIH Esophagus Score 0 after previous involvement	Decrease in NIH Esophagus Score by 1 or more points	Increase in NIH Esophagus Score by 1 or more points, except 0 to 1
Upper GI	NIH Upper GI Score 0 after previous involvement	Decrease in NIH Upper GI Score by 1 or more points	Increase in NIH Upper GI Score by 1 or more points, except 0 to 1
Lower GI	NIH Lower GI Score 0 after previous involvement	Decrease in NIH Lower GI Score by 1 or more points	Increase in NIH Lower GI Score by 1 or more points, except from 0 to 1
Liver	Normal ALT, alkaline phosphatase, and Total bilirubin after previous elevation of 1 or more	Decrease by 50%	Increase by 2 × ULN
Lungs	- Normal %FEV1 after previous involvement - If PFTs not available, NIH Lung Symptom Score 0 after previous involvement	- Increase by 10% predicted absolute value of %FEV1 - If PFTs not available, decrease in NIH Lung Symptom Score by 1 or more points	- Decrease by 10% predicted absolute value of %FEV1 - If PFTs not available, increase in NIH Lung Symptom Score by 1 or more points, except 0 to 1

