11.2.3 Signs and symptoms of cGvHD at baseline

Derivation

Derived variable	Definition
Liver score	
The liver score is defined as a combination of Total bilirubin, ALT (SGPT) and AP (ALK) as follows:
 
Score 0: Normal total bilirubin and ALT < 3 ULN and AP < 3 ULN
 
Score 1: Normal total bilirubin with ALT ≥ 3 to 5 ULN or AP ≥ 3 to 5 ULN
 
Score 2: Elevated total bilirubin (> 1 ULN) but ≤ 3 mg/dL or ALT ≥ 5 ULN or AP ≥ 5 ULN
 
Score 3: Elevated total bilirubin > 3 mg/dL
 
Missing if at least one missing serum chemistry

Involved sites number	Number of sites or organs with a score ≥ 1 at baseline (V1)

The following table will be presented:

Variable	Statistics / Modality	Safety Population (N = XX)
NIH scoring of cGVHD		
Scoring of chronic GVHD (NIH criteria)	
Score 0: Asymptomatic and fully active (ECOG 0, KPS or LPS 100%)
 
Score 1: Symptomatic, fully ambulatory, restricted only in physically strenuous activity (ECOG 1, KPS or LPS 80-90 %)
 
Score 2: Symptomatic ambulatory, capable of selfcare,
	
n/N (XX.X%)
 
n/N (XX.X%)
 
n/N (XX.X%)

	> 50 % of walking hours out of bed (ECOG 2, KPS or LPS 60-70 %)	
	Score 3: Symptomatic, limited self-care > 50 % of waking hours in bed (ECOG 3-4, KPS or LPS < 60 %)	n/N (XX.X%)
	Missing	n
Skin – Abnormalities present but explained entirely by non-GvHD documented cause	No	n/N (XX.X%)
	Yes	n/N (XX.X%)
	Missing	n
	Score 0: No BSA involved	n/N (XX.X%)
	Score 1: 1-18% BSA	n/N (XX.X%)
Skin score	Score 2: 19-50% BSA	n/N (XX.X%)
	Score 3: > 50% BSA	n/N (XX.X%)
	Missing	n
Mouth – Abnormalities present but explained entirely by non-GvHD documented cause	No	n/N (XX.X%)
	Yes	n/N (XX.X%)
	Missing	n
	Score 0: No symptoms	n/N (XX.X%)
	Score 1: Mild symptoms with disease signs but not limiting oral intake significantly	n/N (XX.X%)
Mouth score	Score 2: Moderate symptoms with disease signs with partial limitation or oral intake	n/N (XX.X%)
	Score 3: Severe symptoms with disease signs on examination with major limitation or oral intake	n/N (XX.X%)
	Missing	n

Lung – Abnormalities present but explained entirely by non-GvHD documented cause	No	n/N (XX.X%)
	Yes	n/N (XX.X%)
	Missing	n
Lung score + FEV1	Score 0: No symptoms	n/N (XX.X%)
	Score 1: Mild symptoms (shortness of breath after climbing one flight of steps)	n/N (XX.X%)
	Score 2: Moderate symptoms (shortness of breath after walking on flat ground)	n/N (XX.X%)

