17. APPENDICES

17.1 RESPONSE CALCULATION ALGORITHM

Etude GMED_16_001 : Evaluation des réponses complètes et partielles – 19/10/2020

Les réponses sont définies comme (règles de calcul basées sur le protocole et l'article Lee et al)

- Complete response at a visit: Lorsque tous les scores de « cGVHD activity assessment form A » des organes suivants sont à 0 ou que la variable "abnormalities present but explained entirely by non-GVHD documented cause » soit égale à Oui.

Détails :

Si une valeur est manquante pour un des organes atteints lors de la visite V1, la réponse ne peut pas être considérée comme complète. le fait que la valeur est manquante sera documentée.

Si une valeur à la visite d'intérêt est manquante sur un organe non atteint lors de la visite V1, la réponse complète peut être établie, car les réponses complètes ou partielles ne sont établies que sur les organes atteints à V1.

Si « abnormalities present but explained entirely by non-GVHD documented cause » = Oui pour un organe à la visite considérée, le score de cet organe n'est pas corrigé et cet organe n'est pas considéré pour l'évaluation de la réponse complète. cela ne créera pas de valeur manquante pour cet organe et n'empêchera pas la réponse d'être considérée comme complète si les informations sur les autres organes sont disponibles.

- BSA=0 ET skin features=0

M6_GVHD_A_S (préfixe M6 ou C1W6, W14, M9 et M12 selon la visite considérée)

M6_GVHD_A_S_F_S

M6_GVHD_A_S_ABN

- Eyes=0

M6_GVHD_A_E

M6_GVHD_A_E_ABN

- Gastrointestinal=0 (pour chacun des 3 scores : Gastro-oesophageal, Gastro-upper, Gastro-lower)

M6_GVHD_A_GASTRO1

M6_GVHD_A_GASTRO2

M6_GVHD_A_GASTRO3

M6_GVHD_GAST_ABN

- Mouth=0 (considérer la somme des 3 scores : Erythema, Lichenoid, Ulcers)

M6_GVHD_A_MOUTH1
 M6_GVHD_A_MOUTH2
 M6_GVHD_A_MOUTH3
 M6_GVHD_MTH_ABN

Joint and fascia =0

M6_GVHD_A_J
 M6_GVHD_A_J_ABN

Liver : les 3 valeurs (Bilirubine, ALAT et PAL) sont en dessous des ULN (Unité limite supérieure) si le score hépatique était >0 à V1 (table 1 et annexe du protocole)

.<M6_GVHD_A_L_SGPT_V<=M6_GVHD_A_L_SGPT_U_V
 .<M6_GVHD_A_L_ALK_V<=M6_GVHD_A_L_ALK_U_V
 M6_GVHD_LIV_ABN

Le score à V1 est calculé comme :

Score = 0 : Bilirubine normale WITH ALAT AND PAL < 3 UNL

(.<V1_GVHD_A_L_BILI_V<=V1_GVHD_A_L_BILI_U_V et
 .<V1_GVHD_A_L_SGPT_V<3* V1_GVHD_A_L_SGPT_U_V et
 .<V1_GVHD_A_L_ALK_V<3* V1_GVHD_A_L_ALK_U_V)

Score = 1 : Bilirubine normale WITH 3 UNL<=ALAT < 5 UNL AND 3 UNL <=PAL<5 UNL

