Score = 2 : Bilirubine élevée (>1*ULN) mais <= à 3 mg/dL OR ALAT >= 5 UNL OR PAL >=5 UNL (non mentionné dans article NIH).

Score = 3 : Bilirubine élevée > à 3 mg/dL

Lung : si FEV1 >=80% et FEV1<70 à V1. et dans le cas où la valeur de FEV1 est manquante, si le score est égal à 0

M6_GVHD_A_LU_FEV1_V>= 80
 missing(M6_GVHD_A_LU_FEV1_V) and M6_GVHD_A_L=0
 M6_GVHD_A_L
 M6_GVHD_A_L_ABN

Calcul de réponse par organe :

Aucun calcul de réponse **par organe** (complète, partielle ou progression) n'est effectué si :

- « abnormalities present but explained entirely by non-GVHD documented cause » = Oui pour un organe à la visite considérée
- CR_*organe*, PR_*organe* et PD_*organe* sont alors mis à . (manquant)

Aucun calcul de réponse complète ou partielle **par organe** n'est effectué si :

- l'organe n'est pas atteint à V1 ou abnormalities present but explained entirely by non-GVHD documented cause » = Oui pour un organe à la visite V1.
- la progression est recherchée même si pas d'atteinte à V1
- CR_*organe* et PR_*organe* sont alors mis à . (manquant)

- **Partial response by organ:** en se basant sur les mêmes scores et en s'intéressant aux diminutions (ou augmentations) entre V1 (mêmes variables qu'indiquées précédemment mais qui commencent par « V1 » au lieu de « M6 ») et la visite considérée (M6, W6, W14, M9 ou M12)

- une diminution d'1 point pour les scores sur des échelles de 0 à 4 pour : Skin BSA, Skin features, Eyes, Joints, Gastro-oesophageal, Gastro-upper, Gastro-lower,
- une diminution de 2 points pour la somme des 3 sous-scores pour Mouth
- pour Lung, une augmentation entre V1 et la visite d'au moins 10% sur FEV1 avec FEV1 à V1 <70. Dans le cas de FEV1 manquants à V1 et ou M6, une diminution d'1 point sur le score 'lungs'
- pour Liver, (Bilirubine, ALAT ou PAL),
- si les valeurs à M6 sont en dessous des normales, la réponse est considérée Complète
- sinon la recherche d'une réponse partielle est effectuée : diminution de 50% de la valeur initiale
 Le ratio est calculé ainsi : $(M6-V1/V1)*100$ et si le ratio est inférieur à -50 (mais pas de progression pour une des autres valeurs), il y a une réponse partielle

Global Partial response: au moins une réponse partielle sur un organe et avec une absence de progression pour un autre site

- **Progressive disease by organ:**

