- peau, yeux, œsophage, tractus gastro-intestinal supérieur et inférieur : augmentation 1 point ou plus sur échelle de 0 à 3 = progression SAUF si changement de 0 à 1 (progression non spécifique)
- Joint: augmentation d'1 point ou plus = progression
- bouche : changement de 2 points ou plus sur la somme des 3 sous-scores

- pour Lung, diminution de 10 % avec FEV1 à V1 < 75% . Dans le cas de FEV1 manquants, augmentation d'1 point ou plus *SAUF* si changement de 0 à 1 (progression non spécifique)

- pour Liver, si l'une des valeurs à M6 est au-dessus de la normale pour Bilirubine, ALAT ou PAL, la recherche d'une progression est effectuée : la différence M6 – V1 est calculée et si la différence est supérieure à 2*ULN, il y a Progression.

Global progressive disease : si au moins un site avec une progression

Mixed response: si **Progressive disease** sur au moins un organe et **Partial response** sur au moins un autre

Extraits du protocole :

Table 4. Response determination for chronic GvHD (extrait du protocole)

Organ	Complete Response	Partial Response	Progression
Skin	NIH Skin Score 0 after previous involvement	Decrease in NIH Skin Score by 1 or more points	Increase in NIH Skin Score by 1 or more points, except 0 to 1
Eyes	NIH Eye Score 0 after previous involvement	Decrease in NIH Eye Score by 1 or more points	Increase in NIH Eye Score by 1 or more points, except 0 to 1
Mouth	NIH Modified OMRS 0 after previous involvement	Decrease in NIH Modified OMRS of 2 or more points	Increase in NIH Modified OMRS of 2 or more points
Esophagus	NIH Esophagus Score 0 after previous involvement	Decrease in NIH Esophagus Score by 1 or more points	Increase in NIH Esophagus Score by 1 or more points, except 0 to 1
Upper GI	NIH Upper GI Score 0 after previous involvement	Decrease in NIH Upper GI Score by 1 or more points	Increase in NIH Upper GI Score by 1 or more points, except 0 to 1
Lower GI	NIH Lower GI Score 0 after previous involvement	Decrease in NIH Lower GI Score by 1 or more points	Increase in NIH Lower GI Score by 1 or more points, except from 0 to 1
Liver	Normal ALT, alkaline phosphatase, and Total bilirubin after previous elevation of 1 or more	Decrease by 50%	Increase by 2 × ULN

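### SAP 17.1 counts a fall in either skin sub-score as skin partial response, while the endpoint tables use one NIH Skin Score, so computed partial response can exceed the defined endpoint

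*SAP*

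**What the plan says.** **Endpoint definition.** SAP 8.2.1 and Protocol Table 4 judge skin on a single score. PR is "Decrease in NIH Skin Score by 1 or more points" and progression is "Increase in NIH Skin Score by 1 or more points, except 0 to 1". SAP 17.1 reproduces the same table.

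**How the two skin scores combine.** The footnote to Protocol Appendix 2 says that when the BSA and feature scores disagree, "the higher level should be used for the final skin scoring". Protocol 9.2 is narrower: "The higher of the 2 scores is to be used for computation of global severity". Protocol 7.1.2 and the key points under Table 3 also give the rule for global severity.

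**The algorithm in SAP 17.1.**
- Complete response (CR) needs "BSA=0 ET skin features=0".
- PR needs a 1-point fall among "Skin BSA, Skin features, Eyes, Joints, Gastro-oesophageal, Gastro-upper, Gastro-lower". The two skin items are listed separately and no combined skin score is defined.
- Progression names skin once, as peau, on a 0 to 3 scale: "peau, yeux, œsophage, tractus gastro-intestinal supérieur et inférieur : augmentation 1 point ou plus sur échelle de 0 à 3 = progression", with a change from 0 to 1 exempted. The rule does not say which skin score is meant.
- Global PR needs a PR in at least one organ and no progression at another site.

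**Where the algorithm is used.** It supplies the computed response in sensitivity analyses 11.4.1.2 b and d, the response-by-organ table (11.4.2.1) and the progression event in 11.4.2.2 b. The main analysis (11.4.1.1) uses the investigator's judgement.

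**The concern.** The algorithm is meant to apply the endpoint definition without judgement. For skin PR it applies a looser rule: either component may fall, even when the component that sets the NIH Skin Score has not moved. The case that matters is sclerotic skin. The extent of rash can recede while hidebound skin stays at the top feature score, and that patient is a skin PR by algorithm but unchanged by the endpoint table.

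Because one organ PR is enough for global PR, such a patient can become a computed responder. The trial is single-arm and unblinded, and analyses b and d are the only ones that replace the investigator's judgement with a rule. If that rule errs towards response, it is a weaker check than it appears to be.

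Elsewhere 17.1 does combine sub-scores first: the three mouth scores are summed before the 2-point threshold is applied. Skin gets no such step, although the response-by-organ table has one skin result per patient.

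**Working it through.** The plan states no figure on this point, so there is none to reproduce. The check lists every possible change in the two skin scores and classifies it under each rule.

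**Inputs**
- BSA score B: 0, 1, 2, 3. Skin-features score F: 0, 2, 3, with no level 1 (SAP 11.4.2.5).
- Skin must be involved at V1, because 17.1 computes CR and PR only for organs involved at V1.

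**Rules compared**
- Endpoint table with the Appendix 2 footnote: S = max(B, F). PR if S falls by 1 or more; progression if S rises by 1 or more, except 0 to 1.
- SAP 17.1: PR if B falls by 1 or more, or F falls by 1 or more. Progression is first read on S, as the single word peau allows. A pattern that is progression on S is counted as progression.

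**Number of patterns**
- Unrestricted: 4 × 3 = 12 states, 11 of them with skin involved, so 11 × 12 = 132 transitions.
- If features above 0 imply B of at least 1, the states (0,2) and (0,3) drop out: 10 states, 9 involved, 9 × 10 = 90 transitions.

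| | Features imply B ≥ 1 | Unrestricted |
|---|---|---|
| Transitions | 90 | 132 |
| Either sub-score falls (17.1) | 54 | 84 |
| S falls (endpoint table) | 32 | 45 |
| Extra patterns | 54 − 32 = 22 | 84 − 45 = 39 |
| of which progression on S | 4 | 10 |
| PR under 17.1, S unchanged | 22 − 4 = 18 | 39 − 10 = 29 |
| of which the other sub-score does not rise | 8 | 13 |

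S cannot fall unless the sub-score that sets it falls, so no pattern is PR on S without being a fall under 17.1. On this reading the error runs one way only, towards PR.

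**Examples, as (B, F)**
- (3,3) to (2,3): S stays at 3, unchanged; 17.1 gives skin PR.
- (1,2) to (0,2), which arises only in the unrestricted set: S stays at 2; 17.1 gives skin PR.
- (1,3) to (3,2): S stays at 3. F falls and B rises, and 17.1 has no rule for opposite movements within skin.

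**CR.** Both scores are 0 exactly when their maximum is 0, so skin CR is the same under either rule.

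**If progression were also scored on each sub-score.** Patterns in which the other score rises would become progression. The PR-versus-unchanged patterns would fall to 8 of 90 (13 of 132). A further 4 + 18 = 22 of 90 (7 + 27 = 34 of 132) would be progression under 17.1 where S shows PR or no change. The totals would then be 30 of 90 and 47 of 132. The 8 and 13 are misclassified as PR under both readings.

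**The case against.** **The higher-of-two rule is not in the endpoint tables.** This is true. Protocol 7.1.2, Table 3 and 9.2 tie it to global severity, and Form A collects the two scores with no combined field shown. SAP 17.1 also says that it draws on a published response-criteria article, which is not available here. What stands is that the rule for response is an inference. It is a strong one: the tables name one NIH Skin Score, the Appendix 2 footnote is the only general instruction for forming it, and neither document offers another.

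**Progression.** A reader might infer that computed progressors, and so the progression-free survival events in 11.4.2.2 b, also depart from the definition. The text does not show this. The reference in 17.1 to using the same scores stands under the PR rule. The progression rule names skin once, unsplit, and 17.1 reprints the single-score table. The defect there is an unstated score. The totals of 30 of 90 and 47 of 132 depend on the split reading and should not be quoted as the size of the problem.

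**Effect on the trial result.** A reader might also infer that one or two patients with sclerotic skin could carry the computed result across 17 of 21. That is unsupported. The documents give no number of such patients, and analyses b and d repeat the exact confidence interval of 11.4.1.1, not a count against 17. A false skin PR changes global response only if no other organ responds and no other site progresses.

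**Conclusion.** The point holds for skin PR. As written, SAP 17.1 can record a skin PR where the NIH Skin Score has not changed, and so can overstate global PR in analyses 11.4.1.2 b and d and skin response in the response-by-organ table.

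The size is 18 of 90 possible transitions (29 of 132 unrestricted) with progression on the single score. It is at least 8 of 90 (13 of 132) if progression is split. These count patterns with equal weight and say nothing about how many patients show them.

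The conclusion rests on taking the NIH Skin Score as the higher of the two scores, and on reading the 1-point fall in 17.1 as applying to each listed item. Skin CR and the main investigator-judged analysis are unaffected. An effect on progressors and on progression-free survival is possible but not shown. This is a correction to supporting analyses, worth making before they are run.

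**What to change.** In SAP 17.1, derive SKIN = max(BSA score, skin-features score) at V1 and at each visit. Skin PR is a fall in SKIN of 1 or more; skin progression is a rise of 1 or more, except 0 to 1. CR stays as written. This also names the score used for progression and settles cases where the two scores move in opposite directions. Keep the two sub-scores as descriptive rows.

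Optionally, tabulate SKIN at baseline in SAP 11.2.3. The skin score there is BSA only ("Score 1: 1-18% BSA"), so deep sclerosis over 10% of body surface appears as score 1. The involved-sites count changes only if a patient has features scored with a BSA score of 0.

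The cost is a few lines of SAP text and one derived variable. Both sub-scores are already collected on Form A, so no new data are needed.

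### In SAP 17.1 the liver partial-response ratio drops the baseline value and the mouth progression rule has no direction, so coding either as printed misclassifies the computed response

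*SAP*

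**What the plan says.** SAP 17.1 gives, in French and with named database variables, the rules for computing response at month 6 (M6) against baseline (V1).

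- **Liver.** Complete response is tested first: "si les valeurs à M6 sont en dessous des normales, la réponse est considérée Complète" (M6 values below the upper limits of normal, ULN). Only otherwise is PR sought. Its aim is "diminution de 50% de la valeur initiale", a 50% decrease from the initial value. The ratio is printed as `(M6-V1/V1)*100`, and PR follows "et si le ratio est inférieur à -50", with the proviso "mais pas de progression pour une des autres valeurs" (no progression in one of the other values). No organ CR or PR is computed if "l'organe n'est pas atteint à V1" (organ not involved at V1).
- **Mouth.** PR is a fall of 2 points in the sum of the erythema, lichenoid and ulcer subscores. Progression is "bouche : changement de 2 points ou plus sur la somme des 3 sous-scores", a change of 2 or more points in that sum. The response table in SAP 8.2.1, repeated in 17.1 as Table 4, has "Increase in NIH Modified OMRS of 2 or more points". Protocol 9.3 speaks of worsening.
- **Combining organs.** Global PR needs PR in one organ and no progression at another site. One progressing site makes global progressive disease (PD). PR in one organ with progression in another is a mixed response.
- **Use.** The computed response feeds sensitivity analyses b and d (SAP 11.4.1.2). The by-organ table (11.4.2.1) and progression-free survival (PFS, 11.4.2.2 b) also rest on this appendix. The main analysis (11.4.1.1) uses the investigator's judgement.

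**The concern.** This appendix is what a programmer would code. As printed, the liver ratio is not a percentage change, and the mouth rule treats improvement as worsening.

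The trial is single-arm and unblinded, and its main result is the investigator's own call. The computed response is the plan's rule-based check on that call. If the rules are wrong, agreement or disagreement between the two cannot be interpreted. PFS is also exposed, because its event is the global PD of this appendix.

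**Working it through.** **Inputs.** The ratio and threshold are those printed in SAP 17.1. Form A (Protocol Appendix 8) records bilirubin in mg/dL and ALT and alkaline phosphatase in U/L. The mouth score runs from 0 to 12 (Protocol 9.2). The documents give no numerical ULNs. I assume 40 U/L for ALT, 120 U/L for alkaline phosphatase and 1.2 mg/dL for bilirubin.

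**1. The plan's own figure.** A 50% fall should give -50. Take ALT 300 to 150 U/L.
- As printed: (150 - 300/300) x 100 = (150 - 1) x 100 = +14900. The stated figure is not reproduced.
- With the bracket: (150 - 300)/300 x 100 = -50.0. It is reproduced, but a strict below -50 still excludes a fall of exactly 50%.

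Since V1/V1 = 1, the printed ratio is always (M6 - 1) x 100. It is below -50 only when M6 < 0.5, whatever V1 was.

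**2. A missed PR.** ALT falls from 300 to 120 U/L, with bilirubin steady at 0.8 mg/dL and alkaline phosphatase steady at 100 U/L.
- Involvement: 300/40 = 7.5 x ULN, so the V1 liver score is 2. This holds for any ALT ULN up to 300/5 = 60 U/L.
- CR gate: 120 U/L is still above ULN, so CR fails and PR is sought.
- As printed: (120 - 1) x 100 = +11900, not PR. Bilirubin gives -20 and alkaline phosphatase +9900, so neither rescues it.
- With the bracket: (120 - 300)/300 x 100 = -60, PR.

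**3. A false PR.** ALT is unchanged at 240 U/L (6 x ULN), bilirubin unchanged at 0.4 mg/dL and alkaline phosphatase unchanged at 100 U/L.
- The liver is involved, not in CR, and nothing progresses.
- As printed, bilirubin gives (0.4 - 1) x 100 = -60, so the liver is PR although nothing moved.
- With the bracket, all three ratios are 0 and there is no PR.

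**4. Mouth.** There are 13 x 13 = 169 pairs of V1 and visit scores. Removing the 13 with no change and the 24 that differ by 1 leaves 132 that differ by 2 or more: 66 rises and 66 falls.

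| Rule for mouth progression | Pairs called progression | Of these, also meeting mouth PR |
|---|---|---|
| 17.1 as printed (change) | 132 | 66 |
| Table 4 (increase) | 66 | 0 |

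The 66 extra pairs are exactly the improvements of 2 or more points. These are counts of score pairs, not of patients.

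**5. Effect on the global result, mouth rule as printed.**
- Skin PR plus a mouth fall of 2 or more points becomes a mixed response, so the patient is not a computed responder.
- Mouth PR alone, with no progression elsewhere, is both global PR and global PD.
- A complete responder whose mouth score fell from 4 to 0 is also global PD, hence a PFS event.

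**6. A separate gap.** Keep ALT at 240 U/L and let bilirubin fall from 1.0 to 0.4 mg/dL, normal at both visits under the assumed ULN. The bracketed ratio is (0.4 - 1.0)/1.0 x 100 = -60, so the liver is PR while the abnormal test has not moved. Involvement is judged for the organ, not for each test.

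**The case against.** The best defence is that the intent is printed beside both slips. The 50% aim stands just before the ratio, the threshold is -50, and Table 4 in the same appendix gives a 50% decrease. The mouth rule sits under a progression heading, and the same list uses *changement* for a worsening from 0 to 1. A careful programmer might code both rules correctly, and the documents do not show the code. The formula was also read from a PDF by a program, so the bracket could have been lost there. All of this stands. It makes the errors easy to repair, but a programming specification should not depend on the reader overriding it. The mouth wording does not depend on the bracket, and every other organ in that list has a direction.

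A reader might infer that liver responses vanish altogether. They do not: CR is tested first and never uses the ratio. ALT 200 to 40 U/L, or bilirubin 2.4 to 0.8 mg/dL, is a lost PR only if that test or another remains above its ULN. If all three are normal, the liver is CR.

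A reader might also call the case in step 6 an error. The documents do not support that. Protocol Table 4 likewise gives liver PR as a 50% decrease, without saying which test must fall. Only its CR cell mentions a prior elevation: "Normal ALT, alkaline phosphatase, and Total bilirubin after previous elevation of 1 or more". The SAP follows the protocol here, so this is a shared gap.

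**Conclusion.** Both rules are wrong as printed and contradict the SAP's own definitions. The liver ratio ignores baseline, so it can miss a true PR and create a false one. The mouth rule makes every improvement of 2 or more points a progression as well. The conclusion on the bracket assumes that the original PDF reads as the extracted text does. The misclassifications follow only if the rules are coded literally. The liver examples rest on the assumed ULNs.

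It would be too strong to infer that the primary result is wrong, since the main analysis takes the investigator's response and does not use these rules. Nor can a size in percentage points be stated. One patient in 24 is 4.2 points, but efficacy is analysed on the full analysis set, limited to patients who completed cycle 1 and had a Week 6 evaluation, and that number is not given. Analysis d also removes three named patients. How many patients had a liver or mouth pattern that triggers either error cannot be derived from the documents.

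The correction should be made before the computed response and PFS are relied on.

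**What to change.** In SAP 17.1:

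1. Liver PR: write `((M6-V1)/V1)*100 <= -50`, after checking the bracket against the original PDF. The `<=` makes a fall of exactly 50% count, in line with the stated aim.
2. Mouth progression: replace *changement* with *augmentation de 2 points ou plus*, measured from V1 on the summed score.
3. Run the code on worked cases, including those in steps 1 to 3 and 5 of the working.
4. As a separate decision, the sponsor should state whether a fall in a liver test that was normal at V1 can count as liver PR while another test stays raised, and carry the answer into both the SAP and protocol Table 4.

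Items 1 and 2 cost two short edits and the matching lines of code. Item 3 is a brief programming check. Item 4 clarifies a response definition, so it needs a documented sponsor decision. If any affected output already exists, it should be rerun and the change recorded as SAP 12.5 requires.
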